We performed a follow-up analysis of data from Health and Retirement Study waves 2004 and 2006, including respondents aged ≥ 51 years in 2004 (n=18,908). We examined the prevalence and two-year cumulative incidence of eight geriatric conditions (cognitive impairment, falls, incontinence, poor nutrition, dizziness, vision impairment, hearing impairment, pain) and their association with diabetes. We found that adults with diabetes, compared to those without, had increased prevalence and incidence of geriatric conditions across the age spectrum ($p<.01$ for all ages through 75-79 years old). Diabetes was associated with the two-year cumulative incidence of acquiring new geriatric conditions (OR= 1.7, 95%CI 1.3-2.2).

→ Middle-aged adults, as well as older adults with diabetes are at increased risk for the development of geriatric conditions, which contribute substantially to their complex health status. These findings provided support for our study to include middle-aged veterans, and tailor our intervention to accommodate their complex health conditions and the contextual environment (physical and social).

METHODS

Study Design

This is a randomized-controlled trial to test the efficacy of a tailored lifestyle-based PA intervention, among veterans aged ≥ 60 years with diabetes. The study will compare the intervention group with a wait-list control group (**AIM 2**), where **AIM 1** will assess the baseline information for both the intervention group and wait-list control group, and **AIM 3** will assess the subjects' experience of the intervention to prepare for a larger randomized trial in the future.

SAMPLE SIZE: N=70

Recruitment

Setting:

The study will take place at the main campus of VA Ann Arbor Health System, located in Ann Arbor, which serves nearly 57,000 Veterans living in a 15-county area of Michigan and northwest Ohio (fiscal year 2011). More than 455,000 outpatient visits were made at VAAAHS in fiscal year 2011. According to national VHA data, at least 16% veterans are expected to have diabetes and more than 70% of veterans are either overweight or obese; obesity is a single major risk factor for diabetes.⁶⁰ According to CDC estimates, 27% of adults aged ≥ 65 have diabetes;¹ thus, similar number of veterans with diabetes is expected.. We will primarily recruit subjects from 4 resources:

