2. The research assistant (RA) will guide the participants to complete a packet of survey questions. The questionnaires will ask about demographics, co-morbidities, physical activity (self-reported), *social participation*, their perception of the influence of contextual environment (physical and social environment) on daily lives, and potential barriers and facilitators of diabetes care.
3. The RA will direct the participants to complete a standardized education module, where they will learn to use the wrist-worn accelerometer to rate their response to pre-determined questions using a numerical

rating scale and entering responses, and to record addition information on activities and /or barriers or facilitators to PA in an accompanying logbook. [name] group has already refined this education module to teach older veterans with osteoarthritis and low back pain to use a similar accelerometer and logbook to obtain data on PA and symptoms. We will adapt [name] education module for this study. The accelerometers are designed for assessment of PA patterns over time and will be worn by each participant in their home environment for 7 continuous days (allowing capture of data on both weekdays and weekends). At five pre-determined times throughout the day, the accelerometers will prompt the participants to enter responses to 3 pre-determined questions to assess their perception of the contextual environment on their ability to participate in PA and social activities (i.e., momentary assessment of the environment). Based on experience by [name] group, we will set the accelerometer alarm at wake up time, 11am, 3pm, 7pm, and before bedtime. Time for waking up and going to bed will be individualized for each participant. Each participant will know when their accelerometer alarm will go off. This will help the participant to pay attention to the alarm.

- Participants will become familiar with an accompanying logbook, in which participants will record the exact environment and activities they were involved in at two-hour intervals (See Appendix for the mock Activity Log). The logbook provides supplementary data that are important for the tailoring intervention, and also serves to cross-validate the items entered in the accelerometer. The logbook will be used as a back-up if there are missing data from the accelerometer.

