The wrist-worn accelerometer will be mounted on each participant's non-dominant wrist. Although it is worn on the wrist, it is highly associated with whole-body movement.^{72,73} Changes in acceleration are recorded as activity counts and saved every 15 seconds. Higher activity counts reflect participation in higher intensity activities.^{74,75} Actiwatch has been shown to have excellent reliability between units ($r = .98$) and has established preliminary criterion validity among a sample of chronic pain patients.⁷⁶ Three main PA measurements are derived from the Actiwatch: 1) average activity counts/minute reflects average level of PA over a specified time period; 2) peak PA (largest daily activity count averaged over 7 days) is a measure of daily activity intensity; and 3) total PA is the 7-day cumulative activity score at times when a person was deemed awake and excluding missing data that occurred from temporary removal of the Actiwatch. We will look at average activity counts and total activity counts that occur: 1) in different context, 2) over each day, and 3) over the 7 day period. Because participants wear the accelerometer continuously for 7 days, it is necessary to establish participants' wake-up and bedtimes. A previously-established algorithm will be used to corroborate participant-report of wake and bedtimes with the objective measures.

2. Physical activity will also be self-reported by having the study participants completing the *Community Healthy Activities Model Program for Seniors (CHAMPS)* questionnaire.⁷¹ CHAMPS is a self-administered questionnaire developed for underactive populations and tested primarily among older adults. The questionnaire included 41 items, asking the respondent to report the participation in specific activities that older adults are likely to engage in. The responses are "YES" or "NO" to an activity, and if "YES", then the

number of times per week and total hours per week of activity participation. From the questionnaire, we can derive measures of frequency per week and estimated caloric expenditure per week in PA. For both frequency and caloric expenditure, two measures can be derived based on: 1) PA of moderate or greater intensity (MET value ≥ 3.0), and 2) all specified PA that included activities of light intensity in addition to moderate and greater. The 6-month reliability coefficients for total and moderate-intensity activities were 0.66 and 0.76, respectively.⁷¹

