Hypothesis 1: Lower levels of weekly and daily PA will be associated with a greater number of physical and social environmental barriers and less social participation.

Since PA is measured by Actiwatch objectively and self-reported by CHAMPS, we will first compare them with correlation analyses and identify the correlation coefficient. We will then use separate linear regression models to evaluate if environmental barriers (MQE) and social participation (PROMIS) predict PA, adjusting for baseline co-variates and potential confounders. Separate models will be used for the two different PA measurements - CHAMPS and Actiwatch.

Table 5.

Variables	Measures
PA(outcome)	Actiwatch – weekly and daily average counts
	CHAMPS – weekly energy expenditure (kcal/wk)
Environment	MQE – summary score of environment barriers/facilitators
	Momentary assessment – daily perception of environmental barrier (3 questions)
Social participation	PROMISE – summary score of participation ability and satisfaction
	Daily assessment – daily satisfaction with participation (3 questions)

We will then explore if the perception of environment barriers to PA and participation and satisfaction with participation fluctuate daily. Longitudinal analysis models will be built with time as covariate and each of these variables as the outcome. These variables are assessed daily during the home monitoring period by 6 separate questions adapted from validated questionnaires. We expect study participants' answers to some if not all of these questions to vary daily. We will

[figure not shown]
then build separate predictive models using hierarchical linear modeling (HLM) if change in the perception of the environment or satisfaction with participation is associated with PA (Actiwatch daily average counts). The HLMs will allow us to fully utilize the repeated measures of the environment, participation, and PA within each day.

Aim 2: To pilot a randomized-controlled trial to test the efficacy of an individually tailored lifestyle-based PA intervention. An intent-to-treat analysis will be applied to avoid various misleading artifacts that can arise in the trial; all subjects initially enrolled in the trial will be accounted for based on the group they were randomized into. Baseline comparison of the control and intervention groups will be done with ANOVA on PA, participation, and all the co-variates. We will consult our statistician for analysis guidance.

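### The Aim 1 hierarchical model takes one daily PA average as its outcome, so it cannot use within-day repeated measures as claimed, nor estimate the momentary link between surroundings and activity

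*Combined protocol and SAP*

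**What the plan says.** Under Statistical Analysis, Primary analyses, Aim 1, the plan will use HLMs to test whether change in perceived environment or in satisfaction with participation "is associated with PA (Actiwatch daily average counts"). The next sentence reads: "The HLMs will allow us to fully utilize the repeated measures of the environment, participation, and PA within each day". Table 5, in the same section, lists the environment predictor as "Momentary assessment – daily perception of environmental barrier (3 questions"), and the text treats all six momentary and satisfaction questions as daily.

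The data are collected on different time scales:

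- **Environment.** Research Procedures, Baseline data collection, states: "At five pre-determined times throughout the day, the accelerometers will prompt the participants to enter responses to 3 pre-determined questions". The prompts come at wake-up, 11am, 3pm, 7pm and bedtime. The device is "worn by each participant in their home environment for 7 continuous days".
- **PA.** Measures, Primary outcomes a), states: "Changes in acceleration are recorded as activity counts and saved every 15 seconds".
- **Satisfaction.** Measures, Primary outcomes b), has the three ratings entered in the logbook once a day.

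The plan does not say how five prompts become one daily value, or which stretch of counts belongs to which prompt.

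**The concern.** The two adjacent Aim 1 sentences do not fit together. With daily average counts as outcome, the model has days nested in persons, and PA does not vary within a day. The participation items cannot vary within a day either, because they are collected once daily. Only the environment ratings and the raw counts repeat within a day, and the model as written does not link them at that level.

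The quantity estimated is at stake as well as precision. A day-level slope says whether days with worse average ratings are days with lower average activity. A prompt-level slope says whether activity is lower at the times when surroundings are rated as hindering. The two can differ. The second is closer to what the counselling uses: under the intervention section the therapist relates activity to the barrier present at the time, and the treatment fidelity section calls the validity of the momentary information central to tailoring.

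**Working it through.** The plan states no power, effect size, alpha, SD or intraclass correlation for this analysis, so there is no figure to reproduce.

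**Inputs from the documents.** N = 70 ("SAMPLE SIZE: N=70"), D = 7 days, K = 5 prompts a day, and one PA value per person-day in the HLM.

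**Counts, assuming every prompt is answered.**

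- Person-days: 70 × 7 = 490. Prompt records: 70 × 7 × 5 = 2,450.
- Within-person degrees of freedom between days: 70 × (7 − 1) = 420.
- Within-person degrees of freedom within days: 70 × 7 × (5 − 1) = 1,960.
- Share lying within days: 1,960 / (1,960 + 420) = 82%. The daily model does not use these for the environment–PA link.

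**Information on a common within-person slope.** Let rx be the share of within-person variance in the rating that lies between days, and ry the same share for residual PA. Both are assumed.

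- Day level: I_day = N(D − 1) × [rx + (1 − rx)/K] / [ry + (1 − ry)/K]
- Prompt level: I_prompt = I_day + N·D·(K − 1) × (1 − rx)/(1 − ry)

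If the prompt-level test has 80% power at two-sided alpha 0.05 (assumed), day-level power is Φ[(1.96 + 0.84)·√(I_day/I_prompt) − 1.96].

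| rx | ry | I_day | I_prompt | Information kept | Day-level power |
|---|---|---|---|---|---|
| 0 | 0.5 | 140 | 4,060 | 3% | 7% |
| equal to ry | equal to rx | 420 | 2,380 | 18% | 22% |
| 0.5 | 0 | 1,260 | 2,240 | 56% | 56% |
| 0.8 | 0 | 1,764 | 2,156 | 82% | 72% |
| 0.95 | 0 | 2,016 | 2,114 | 95% | 78% |

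The daily model is not necessarily weak. With rx = ry and a standardised slope of 0.1, power is 54% by day and about 100% by prompt. At 0.2 it is 98% and about 100%.

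**Sensitivity to the split of predictor variance.** Take a slope of −0.05 and residual SDs of 1.0 per prompt and 0.5 per day, all assumed.

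- Predictor SD 1.0 within day and 0.5 between days: I_day = 420 × (0.25 + 0.20)/(0.25 + 0.20) = 420. I_prompt = 420 + 1,960 = 2,380. Power is Φ(0.05·√420 − 1.96) = 17% by day and Φ(0.05·√2,380 − 1.96) = 68% by prompt. Simulation with a simpler person-centred regression gives 15% to 19% and 61% to 62%.
- The two predictor SDs swapped: I_day = 420 × (1.00 + 0.05)/0.45 = 980. I_prompt = 980 + 1,960 × 0.25 = 1,470. Power is 35% and 48%. Simulation gives 34% and 43% to 44%.

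Swapping two unknown SDs therefore turns a large loss into a modest one.

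**Is a prompt-level model safe?** Only if time of day is handled. If activity and ratings share a diurnal pattern, a prompt-level slope without a time-of-day term picks it up. With a true slope of zero and assumed patterns of varying strength (lower at wake-up and bedtime), simulated false-positive rates ran from 30% to 100%, while the daily-mean model stayed at 4% to 6%. Fixed effects for prompt slot brought the prompt-level rate back to about 5% and kept power at 62% for the −0.05 slope.

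**The case against.** The strongest defence is that the daily outcome fits the hypothesis. Hypothesis 1 is worded for weekly and daily PA, Table 5 lists daily counts and daily perception, and the text asks whether perceptions fluctuate from day to day. On this view the only fault is one loosely worded sentence. Much of this stands: the daily model is right for Hypothesis 1 and should stay. But even if the sentence only means measurements on each day, the rule for reducing five prompts to one value is still missing.

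The Measures section also plans to look at counts by context. That shows the within-day data are not abandoned, but it gives no window or link to the prompts and is not carried into the HLM. A reader might infer that the plan throws the momentary data away. It does not: the counts and prompts are kept, and each person's tailored report uses them without needing the pooled model.

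A reader might also infer that the daily outcome loses most of the power. The documents do not support that. It depends on variance shares they do not give, and it can be true or nearly false. The calculation above also treats the five prompt windows as representing the day; an average over all waking epochs would have a different error variance.

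Finally, a prompt-level model could do harm. Two of the five prompts sit at the edge of sleep, and time of day can drive both activity and ratings. That objection is correct against a model without a waking-time rule and a time-of-day term. It is met by including both.

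**Conclusion.** The contradiction holds without any assumption: a model of daily averages cannot use PA repeated within a day. For the five-times-daily environment items, it also cannot estimate the moment-to-moment relation with activity.

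The size of the information loss is not determined by the documents. Day-level power is 7% to 78% where prompt-level power is 80%, for rx between 0 and 0.95 and ry between 0 and 0.5. This assumes two-sided alpha 0.05, all prompts answered, and equal slopes within and between days.

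The point is minor. The HLM stands under Primary analyses, but the covariates section calls the momentary information exploratory. The satisfaction items lose nothing, and the randomised Aim 2 comparison is unaffected.

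**What to change.** Keep the daily-average HLM for Hypothesis 1 and for the once-daily satisfaction items, and state how the five prompts are combined into a daily environment value.

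For the momentary environment items, add a prompt-level model with prompts nested in days nested in persons:

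- **Outcome:** mean counts per minute in a window around each prompt. State its length in advance and restrict it to waking time, using the wake and bedtime algorithm already planned under Measures.
- **Time of day:** fixed effects for the five prompt slots.
- **Predictors:** each split into the person mean, the day's deviation from it, and the prompt's deviation from the day.

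Apply the sentence about within-day repeated measures to this model only, and drop participation from it, since those items are rated once a day. Label the model exploratory.

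No new data are needed. The cost is a short change to the analysis text, modest programming to cut the stored epochs into windows, and one more exploratory model to report. If the team does not want that model, the minimum is to correct the sentence and add the aggregation rule.

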Hypothesis 2a: *At the end of 6 months, individuals in the intervention group will have increased PA compared to the control group.* PA is measured in 3 ways using Actiwatch and CHAMPS (Table 5), so three separate analyses will be done using each measure – Actiwatch daily average counts and weekly counts, and CHAMPS weekly measurement.

The primary analysis is based on comparing the 6-month change in PA between treatment group and control group by t-tests. To adjust for potential confounding, separate models of multivariate regression analyses will be conducted with each measure of PA as the dependent variable, randomization arm as a predictor, baseline PA as a covariate, and potential confounders including age, sex, diabetes status, and number and perception of environment barriers will be included in the model. Assuming that residuals from the model fit are normally distributed, the analysis is equivalent to a classical analysis of covariance. For data that does not fit a normal distribution, inverse, logarithmic or power transformations will be performed or generalized linear models (GLM) with Poisson or gamma error will be considered.

To further assess if the pattern of PA changed, i.e., whether the change in PA occurred across each day or just a few days in a week, we will graphically compare the daily average counts at 6-month follow-up for the intervention group with the control group (Figure 5). For example: If Y_{ij} = daily average counts at day_j over 7 days after intervention for subject i and j = 1 (d1), 2 (d2), ..., 7(d7), then we will try to fit the linear mixed model to test if the slopes of the two PA curves are the same and test for overall difference ($\beta_1 = 0$):

$$Y_{ij} = \beta_0 + \beta_1 * \text{intervention} + \beta_2 * \text{days} + \beta_3 * z + \epsilon_{ij}$$

With this small sample of 28-35 participants per treatment group, it is possible that the study may be underpowered to determine significant differences between groups. However, the results will provide essential information about the actual effect size of the treatment which will allow us to better estimate the sample size needed for a larger trial.

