Hypothesis 2b: At the end of 6 months, individuals in the intervention group will have improved social participation (ability to participate and satisfaction with participation). Social participation will be measured with the PROMIS questionnaires with a population mean of 50 and standard deviation of 10. The change in *social participation* will be compared between the treatment and control groups by t-tests, similar to the analysis plan described for *Hypothesis 2a*. Multivariate regression analyses will be conducted to evaluate confounding factors, with social participation as the dependent variable, randomization arm as a predictor, baseline social participation as a covariate. Potential confounders including age, sex, co-morbidities, and number and perception of environment barriers will be included in the model. Distribution of the residuals from model fit will be examined, and additional transformations and generalized linear models will be considered.

Additional analyses:

Further exploration of effects at each time points are of interest. Models will utilize outcome measurements at all time-points (baseline, 5 weeks, and 6 months). Different outcome measures and covariates can be evaluated. Repeated measure longitudinal models can be considered:

For example: **Outcome at 5 weeks and 6 months = BA + G + CF + G*TIME + CF*TIME,**

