where BA=outcome at baseline; G=intervention group; CF= one or more contributing factors; TIME= time variable; *=interaction between variables. The key aspects of this model for hypotheses 2a and 2b are interactions G*TIME and CF*TIME, and the magnitude and significance of these interaction effects provide insight into mechanisms underlying study group differences. The remaining terms are used to reflect study design and adjust for baseline values. This analysis will yield three tests: 1) a test for outcome changes over time of the study, 2) a test of the intervention vs. control group differences (an intervention effect), and 3) a test for interaction of intervention effect with time. As in the primary hypothesis, we are primarily interested in the overall intervention effect. However, a changing intervention effect over time, as reflected in intervention by time interaction is of great interest since it might suggest that the intervention has a greater impact as time progresses, which would provide support for long-term effect of the intervention. The following methods will be considered: linear mixed effects (LME) models for continuous variables with normally distributed residuals; and generalized linear models (GLM). Both of these methods allow for unbalanced data, time-varying covariates, and structured covariance matrices. Repeated measures models will be developed in the framework of linear mixed effects (LME) models or generalized linear mixed effects models (GLMM).

AIM 3: To assess participant satisfaction with the intervention, we will use a series of Likert scale satisfaction items and a semi-structured interview protocol including open-ended questions to obtain feedbacks. A quantitative analysis and a qualitative analysis will be performed for this aim:

- Results from the Likert scale satisfaction items will be analyzed to identify the association between different characteristics of the study participants and their satisfaction with the intervention. Participant characteristics (e.g., age, sex, race, education background, functional status, co-morbidities, etc.) will be cross-tabulated with the satisfaction outcomes, which can be dichotomized into satisfied or not satisfied. Individual relationships will be assessed using χ^2 tests. Multiple logistic analyses will be used to analyze responses according to each factor, controlling for socio-demographic variables.

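### The primary test for Hypotheses 2a and 2b is a t-test of 6-month change, which is less precise than the baseline-adjusted analyses the plan also describes, leaves out the 5-week outcome, and is not covered by the plan's missing-data statement

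*Combined protocol and SAP*

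**What the plan says.** All references are to the combined protocol and SAP.

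- **Hypothesis 2a, primary test.** "The primary analysis is based on comparing the 6-month change in PA between treatment group and control group by t-tests".
- **Hypothesis 2b.** Change in social participation "will be compared between the treatment and control groups by t-tests", by reference to 2a.
- **Adjusted regression.** Both hypotheses then commit to a regression, which for 2a has "randomization arm as a predictor, baseline PA as a covariate", plus further covariates. It is presented as adjustment for confounding, after the t-test.
- **Additional analyses.** "Models will utilize outcome measurements at all time-points (baseline, 5 weeks, and 6 months"). Later in that section: "Repeated measures models will be developed in the framework of linear mixed effects (LME) models". Between these two statements, the repeated-measures model is offered as a possibility and illustrated by an example: "Outcome at 5 weeks and 6 months = BA + G + CF + G*TIME + CF*TIME". The contributing factors (CF) and the covariance structure are left open.
- **Post-intervention assessment.** Drop-out is expected at 6 months, and the 5-week data are described as useful for that reason.
- **Aim 2 analysis.** Intent-to-treat, with everyone enrolled accounted for in the assigned arm.
- **Missing Data.** Baseline variables found to be associated with loss are added as covariates. The section says this gives unbiased effects under MCAR or MAR. No imputation is described. If loss rates differ by arm, only the interpretation changes.

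**The concern.** A change score needs a 6-month value. With no imputation stated, participants without one leave the primary test. This is an inference, since the plan never calls it a complete-case analysis. The test uses baseline only by subtraction, which is less efficient than regression on baseline. It also ignores the 5-week outcome, which the plan values precisely because of drop-out.

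The Missing Data statement works through added covariates. A t-test has none, so the statement cannot cover the primary test. If inference is meant to move to the covariate model, the statement holds only for loss explained by variables in that model, and the 5-week outcome is not among them.

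At stake is the effect estimate that, under Hypothesis 2a, is meant to help size a larger trial. Imprecision or bias in it carries forward, and a confidence interval does not reveal bias.

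**Working it through.** **Inputs from the documents.** N = 70, so 70/2 = 35 per arm, the upper end of the plan's 28-35 per group. 28/35 = 0.80, so the lower end corresponds to 20% loss. That rate is inferred, since none is stated. CHAMPS 6-month reliabilities are 0.66 and 0.76 (Measures). The one effect size cited for participation is 0.16 (background on PA interventions and participation).

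**Assumptions.** Two-sided 0.05, an illustrative 0.5 SD effect, outcome SD = 1 at each visit, and the CHAMPS reliabilities as the baseline-to-6-month correlation r. None is given for Actiwatch or PROMIS. The plan states no alpha, power or design effect, so it has no power figure to reproduce.

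**Precision**

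1. Change score: variance 2(1-r), which is 0.68 at r=0.66 and 0.48 at r=0.76.
2. ANCOVA: variance 1-r², which is 0.564 and 0.422.
3. Ratio ANCOVA/change = (1+r)/2 = 0.83 and 0.88.
4. Standard error at 28 per arm = √(variance × 2/28): t-test 0.220 and 0.185; ANCOVA 0.201 and 0.174.
5. Mixed model, 35 per arm at 5 weeks and 28 at 6 months: variance = (1-r²)[(1-R²)(2/28) + R²(2/35)], where R² is the squared partial correlation of the 5-week and 6-month values given baseline. Correlation sets (baseline-5wk, baseline-6mo, 5wk-6mo) of (.66,.66,.66), (.76,.66,.76), (.70,.66,.85) and (.76,.76,.76) give SE 0.198, 0.195, 0.190 and 0.170.

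Power (noncentral t):

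| | t-test | ANCOVA | Mixed model |
|---|---|---|---|
| 0.5 SD, r=0.66 | 61% | 69% | 70-73% |
| 0.5 SD, r=0.76 | 76% | 81% | 82% |
| 0.16 SD, both r | 11-14% | 12-15% | 12.5-15% |

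Share of the gain due to baseline adjustment, lowest and highest: (.686-.606)/(.734-.606) = 63% and (.686-.606)/(.700-.606) = 85%. Simulated trials with 35 per arm and random 20% loss give the mixed model slightly less: power 0.680-0.809, or 0.003 to 0.038 above ANCOVA.

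**Bias.** Large-sample simulation: 400,000 per arm, no true effect, 20% loss in each arm, the four correlation sets, logit slope 1 or 2 per SD. If loss is random or follows the same mechanism in both arms, all methods are within 0.003 SD of zero. If loss is selective in the intervention arm only and everyone attends at 5 weeks (SD units):

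| Loss depends on | t-test | ANCOVA | Likelihood (mixed) |
|---|---|---|---|
| 5-week change | +0.06 to +0.17 | +0.045 to +0.13 | about 0 |
| 5-week level | 0 to +0.04 | +0.03 to +0.11 | about 0 |
| low baseline | -0.04 to -0.09 | 0 | about 0 |
| 6-month level | +0.04 to +0.09 | +0.07 to +0.16 | +0.05 to +0.13 |

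In the last row the likelihood model is worse than the t-test in three of the four correlation sets and slightly better in one. If half the losses precede the 5-week visit, it is off by +0.015 to +0.06 in the first two rows. Loss rates are equal by arm throughout, so the planned chi-square comparison of rates would not flag these cases, though the comparison of reasons might.

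**The example model as written.** It prints no TIME main effect, yet the text says "This analysis will yield three tests: 1) a test for outcome changes over time of the study"; class coding in the software may supply it. It also says "As in the primary hypothesis, we are primarily interested in the overall intervention effect", which spans both visits, whereas 2a and 2b concern 6 months.

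**The case against.** The strongest reply is that this is largely a choice between valid methods. A change-score t-test is unbiased under randomization with random loss, or with loss that works alike in both arms. The more precise ANCOVA is firmly promised in the same section, so that estimate will be produced anyway. The mixed model adds at most about five power points to it. No method rescues power at an effect of 0.16, and the plan admits that it may be underpowered. All of this stands, and it limits the weight of the point. It does not remove it: the headline result is still the least precise of the three, and the precision gain needs no selective loss.

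Some stronger readings are tempting, but the documents do not support them:

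- **That the plan ignores baseline and 5-week data.** It does not. Both are used, but outside the primary test.
- **That a longitudinal model is ready to be promoted.** It is an illustration, with its contributing factors and covariance open.
- **That the primary result will be biased.** Every non-zero bias above needs selection that differs by arm, and nothing in the documents shows which mechanism will occur.
- **That the mixed model is always safer.** With one-arm loss on the 6-month level it is usually worse than the t-test. With loss on the 5-week level, the t-test is less biased than ANCOVA.

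**Conclusion.** The concern holds as a recommended improvement, not as a finding that the plan is invalid. The textual points are firm: the t-test is primary for both hypotheses, the 5-week outcome is outside it, and the MCAR/MAR statement does not reach a test without covariates. The exclusion of participants without a 6-month value is an inference, though a direct one.

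The assured gain is precision: a 12-17% reduction in variance from baseline adjustment, worth about 5 to 8 power points under the stated assumptions, with a smaller addition from the 5-week data. The possible bias of the t-test, up to about 0.17 SD, is conditional on one-arm selection and lies below that test's own standard error (0.185-0.22 SD). All sizes rest on an inferred 20% loss and on CHAMPS reliabilities as stand-ins for unstated correlations.

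**What to change.** 1. Reconcile the follow-up time points first. The wait-list control section and Table 3 list a 3-month assessment that the participant timeline and the additional analyses omit. If it is collected, include it in the model.
2. Make a baseline-adjusted analysis primary for 2a and 2b. At minimum, promote the planned regression on arm and baseline value. Preferably, turn the example into a specified repeated-measures model: each scheduled follow-up outcome on baseline value, arm, TIME (written explicitly) and arm-by-TIME, with unstructured covariance and all randomized participants who have any follow-up.
3. Name the 6-month arm difference as the primary estimate and fix the covariates in advance.
4. Keep the change-score t-test, and ANCOVA if it is not primary, as sensitivity analyses.
5. Limit the MAR statement to missingness explained by variables in the model. Add a delta-shift sensitivity analysis over all randomized participants, which also covers those with no follow-up. For scale, with 20% missing in one arm, a 0.5 SD shift moves the estimate by 0.20 × 0.5 = 0.10 SD.

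The cost is SAP wording and modest programming, with no new data or visits. The downsides are a less simple headline test, distributional choices to settle in advance for skewed PA data, and continued reliance on MAR.
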